2 INTRODUCTION

2.1 Study Rationale

AZD7442, a combination of 2 mAbs (tixagevimab [investigational name, AZD8895] and cilgavimab [investigational name, AZD1061]), is being developed for the prophylaxis and treatment of COVID-19.

This Phase II dose-ranging study will investigate the safety, immunogenicity, PK, and PD profiles of AZD7442 repeat dosing regimens (600 mg IM on Day 1 then 300 mg IM Q3M and 1200 mg IV on Day 1 then 600 mg IM Q6M) for pre-exposure prophylaxis of COVID-19 in adults and pediatric individuals (≥ 12 years of age weighing at least 40 kg), who are moderately to severely immunocompromised due to an underlying disease or are taking immunosuppressive medications and therefore unable to mount an adequate immune response to COVID-19 vaccine. Pharmacokinetic data will be generated to evaluate the AZD7442 doses and whether repeat dosing can maintain serum levels associated with protection against COVID-19. Pharmacodynamic data will include measurement of neutralizing antibodies levels in serum after AZD7442 repeat dosing.

2.2 Background

Severe acute respiratory coronavirus-2 is the causative agent of the ongoing COVID-19 pandemic that, as of 19 January 2022, has caused over 332 million confirmed cases of COVID-19, including 5.5 million deaths, reported to WHO ([WHO 2022](#)). The majority of CoVs cause mild disease in humans and animals, however SARS-CoV-2 can replicate in the lower respiratory tract to cause acute respiratory distress syndrome and fatal pneumonia. This is also a characteristic of the genetically similar SARS-CoV and the more distantly related MERS-CoV, both of which were responsible for prior outbreaks in 2002 to 2003 and 2012, respectively ([Gorbalenya et al 2020](#)). The original SARS-CoV-2 virus first detected in Wuhan had a basic reproduction number R_0 value estimated between 2.43 to 3.10 and was highly transmissible from person to person, which has contributed to its rapid dissemination worldwide ([D'Arienzo and Coniglio 2020](#)). Mortality risk factors associated with SARS-CoV-2 infection include age > 60 years (significantly greater for those 80 years and older), male sex, and chronic medical conditions, including hypertension, diabetes, obesity, chronic obstructive pulmonary disease, and CV disease ([Zhou et al 2020](#)). Clinical management of COVID-19 is based on supportive care and a limited number of treatment interventions, which results in healthcare resources being stretched ([Tangcharoensathien et al 2021](#)).

As a response to the ongoing pandemic, AstraZeneca has developed mAbs targeting the SARS-CoV-2 spike protein. The SARS-CoV-2 spike protein contains the RBD, which enables the virus to bind to ACE2 receptors on human cells. By targeting this region of the spike protein on the virus, antibodies can block the virus's attachment to ACE2 receptors and, therefore, are expected to block infection. AZD7442 consists of 2 separate mAbs which bind

to distinct, non-overlapping sites on the SARS-CoV-2 spike protein RBD. Binding to either of these sites blocks the virus's ability to bind to ACE2 resulting in a blockade of virus entry, effectively neutralizing the SARS-CoV-2 virus. By blocking virus entry into human cells, AZD7442 stops virus replication, which stops infection, and is, therefore, being developed for the prophylaxis of COVID-19 and treatment of COVID-19.

AZD7442 retains full to nearly full neutralization activity against pseudoviruses and/or authentic SARS-CoV-2 variant strains harboring all spike substitutions identified in circulating variants of concern (including the Omicron BA.2 variant), variants of interest, and variant alerts for further monitoring. For the Omicron BA.1 variant, independent laboratories have generated in vitro potency data showing that AZD7442 maintains neutralizing activity, although increases the IC₅₀ compared to the original SAR-CoV-2 strain were observed ([Dejnirattisai et al 2021](#); [FNIH 2022](#); [VanBlargan et al 2022](#); [Zhou et al 2021](#)). Virological surveillance is ongoing in the clinical studies to characterize how changes in potency observed in authentic SARS-CoV-2 or pseudotyped VLP neutralization assays correlate with clinical outcomes.

The interim analysis for the Phase I FTIH study (D8850C00001; NCT04507256) with AZD7442 in healthy adults indicated that tixagevimab and cilgavimab have a mean terminal $t_{1/2\lambda z}$ of approximately 90 days. The minimum serum protective concentration threshold was reached on average 6 hours (interquartile range of 3.4 to 11.7 hours) after administration of 300 mg AZD7442 and remained above this threshold for 6 months in 96% of participants.

The primary analyses of the Phase III PROVENT (D8850C00002; NCT04625725) and STORM CHASER (D8850C00003; NCT04625972) trials support the use of AZD7442 for prophylaxis of COVID-19. PROVENT met its primary endpoint: AZD7442 administered in a prophylactic setting, before participant exposure to SARS-CoV-2, reduced the incidence of SARS-CoV-2 RT-PCR-positive symptomatic illness by 76.73% compared to placebo, which was statistically significant. In addition, there were no cases of severe COVID-19 or COVID-19 related deaths in the AZD7442 group, compared to 3 cases of severe COVID 19, including 2 COVID-19 related deaths, in the placebo group. STORM CHASER did not meet its primary endpoint: the reduction in risk of developing symptomatic COVID-19 of 33.31% compared to placebo was not statistically significant in this post-exposure to SARS-CoV-2 population. However, in a predefined subgroup analysis, AZD7442 reduced the risk of developing symptomatic COVID-19 by 73.17% in participants with a negative or missing SARS-CoV-2 RT-PCR at baseline. This subpopulation of participants, who had not been exposed to infection prior to receiving AZD7442, is similar to the PROVENT study population.

The primary analysis of the Phase III TACKLE trial (D8851C00001; NCT04723394) supports the use of AZD7442 for the treatment of COVID-19 in non-hospitalized adults. TACKLE met

its primary endpoint with a 50.49% relative risk reduction for developing severe COVID-19 or death compared with placebo in participants dosed ≤ 7 days from symptom onset. Pre-specified analyses showed that this rose to 88.01% and 66.93% relative risk reduction if the participants were dosed ≤ 3 days and ≤ 5 days of symptom onset, respectively. Approximately 90% of trial participants were from populations at high risk of progression to severe COVID-19, including those with co-morbidities.

AZD7442 has generally been well tolerated in the Phase I to Phase III studies. Doses from 300 mg IM (150 mg each of tixagevimab and cilgavimab) to 3000 mg IV (1500 mg each of tixagevimab and cilgavimab) have been administered without dose limiting toxicity.

A detailed description of the chemistry, pharmacology, efficacy, and safety of AZD7442 is provided in the IB.

2.3 Benefit/Risk Assessment

The risks and benefits of AZD7442 are briefly summarized below. More detailed information about the known and expected benefits and potential risks of AZD7442 can be found in the AZD7442 IB.

2.3.1 Risk Assessment

AZD7442 is a combination of 2 human mAbs, with non-overlapping epitopes directed against RBD of the SARS-CoV-2 S protein for neutralization of the virus. Neither mAb has any human target. There are no potential risks based on mechanism of action.

Potential risks based on clinical data include cardiac and thromboembolic events. Due to observations in the adult population in the Phase III pre-exposure prophylaxis study PROVENT (D8850C00002 [NCT04625725]; n = 5197), cardiac ischemia, cardiac failure, and thrombotic events have been included as AESIs in this study. In PROVENT, a numerical imbalance in SAEs in the Cardiac Disorders system organ class was observed between the treatment groups. The number of participants with Cardiac Disorder SAEs adjusted by exposure (in-patient years) were 23 (1.2%) in the AZD7442 group and 5 (0.5%) in the placebo group. In STORM CHASER (D8850C00003; NCT04625972), a Phase III post-exposure prophylaxis study of AZD7442 in adults (n = 1121), which enrolled a younger population with fewer baseline cardiac risk factors than PROVENT, no Cardiac Disorder SAEs were reported. In TACKLE (D8851C00001; NCT04723394), a Phase III outpatient treatment study of AZD7442 in adults (n = 903), there were 2 (0.4%) SAEs in the Cardiac Disorders system organ class in the AZD7442 group and 1 (0.2%) in the placebo group. None of the Cardiac Disorder SAEs in the AZD7442 group were considered related to the investigational product by the investigator. All participants in the Phase III studies who experienced Cardiac Disorder SAEs had numerous cardiac related risk factors and/or a prior history of CV disease at baseline. There was no clear temporal pattern, and a causal relationship between AZD7442

and these events has not been established. The SAEs from SMQ embolic and thrombotic events were also reviewed from these 2 studies (PROVENT and STORM CHASER), and there was no clinically meaningful imbalance in thromboembolic events between participants who received AZD7442 and those who received placebo. Across the cases, many participants had confounding cardiac-related medical histories and risk present at baseline.

The identified risks based on class effect include injection site reactions and hypersensitivity including rash and urticaria. Injection site reactions may be observed and may manifest as local inflammation, redness, itching, pain, bruising, infection, or excessive bleeding at the site of injection. Clinical studies with AZD7442 will closely monitor participants during and after IMP administration. These reactions should be managed according to standard clinical practice.

Potential risks are associated with the administration of any immunoglobulin, including polyclonal immunoglobulin preparations and mAbs. The potential risks include but are not limited to serious hypersensitivity reactions including anaphylaxis, infusion-related reactions, and antibody-dependent enhancement of disease.

An infusion-related reaction is defined as any other reaction (other than hypersensitivity and anaphylaxis) occurring during infusion of IMP or felt to be temporally related to the infusion and occurring within 30 minutes to 2 hours after the initiation of first IMP infusion. However, though less frequent, infusion-related reactions can also occur later on within the first 24 hours from the start of infusion and are less common following subsequent exposures. Infusion-related reactions may manifest with single or multiple signs and symptoms. Most are mild in intensity, but severe and even fatal reactions have been reported. Unlike infusion-related reaction, anaphylaxis is a rare event, usually occurring after subsequent exposure to an antigen, and is most commonly accompanied by severe systemic skin and/or mucosal reactions.

2.3.2 Benefit Assessment

The primary analyses of the Phase III PROVENT (D8850C00002; NCT04625725) and STORM CHASER (D8850C00003; NCT04625972) trials support the use of AZD7442 for prophylaxis of COVID-19. In both the PROVENT and STORM CHASER trials in adults, AZD7442 reduced the risk of developing symptomatic COVID-19 by more than 70% compared with placebo in participants who were SARS-CoV-2 negative at baseline (see Section 2.2).

Despite the rollout of effective SARS-CoV-2 vaccines, there remains a clear unmet medical need to provide effective prophylaxis to neutralize SARS-CoV-2 and ensure protection against emerging variants, particularly in those individuals not expected to mount an adequate

response to complete active immunization (CDC 2021a), and those for whom vaccination is not suitable.

The individuals to be included in this study, adults and pediatric individuals (≥ 12 years old) who are moderately or severely immunocompromised and who may not mount an adequate immune response to COVID-19 vaccination, may benefit from AZD442 repeat dosing regimens for ongoing protection against COVID-19.

2.3.3 Overall Benefit: Risk Conclusion

Considering the measures taken to minimize risk to participants in this study, the potential risks identified in association with AZD7442 are justified by the anticipated benefits that may be afforded to participants who are immunocompromised and at risk of COVID-19.

3 OBJECTIVES AND ENDPOINTS

Table 5 lists the objectives and endpoints for the study.

Table 5 Objectives and Endpoints

Objective	Endpoint
Primary	
To evaluate the safety and tolerability of AZD7442	AEs, SAEs, and AESIs
To evaluate the immunogenicity of AZD7442	Incidence of ADA in serum
Secondary	
To evaluate the PK of AZD7442 in serum	Serum AZD7442 concentrations PK parameters
To determine anti-SARS-CoV-2 nAb levels in serum after administration of AZD7442	Changes from baseline in GMTs and GMFRs values in SARS-CoV-2 nAbs (wild-type assay or pseudo-neutralization assay)
Exploratory	
To estimate the efficacy of AZD7442 for the prevention of COVID-19	Incidence of SARS-CoV-2 RT-PCR-positive symptomatic illness Incidence of participants who have a post-treatment response (negative at baseline to positive at any time post-baseline) for SARS-CoV-2 nucleocapsid antibodies
To estimate the efficacy of AZD7442 for the prevention of severe or critical symptomatic COVID-19	Incidence of SARS-CoV-2 RT-PCR-positive severe or critical symptomatic illness and COVID-19 deaths
To evaluate the PK of AZD7442 in nasal fluid	Nasal AZD7442 concentrations
To quantify SARS-CoV-2 viral loads in infected participants treated with AZD7442 (Illness Visits)	Viral genome copies in NP swabs at Illness Visits as determined by RT-PCR

Table 5 Objectives and Endpoints

Objective	Endpoint
To characterize resistance to AZD7442 (Illness Visits)	Genotypic analysis and biochemical and/or susceptibility analysis of SARS-CoV-2 variants to AZD7442
To assess additional immune responses in participants treated with AZD7442 (Illness Visits)	Other exploratory assays for humoral, mucosal, and cellular immune responses may be performed based upon emerging safety, efficacy, and pharmacodynamic data

ADA, antidrug antibody; AE, adverse event; AESI, adverse event of special interest; COVID-19, coronavirus disease 2019; GMT, geometric mean titers; GMFR, geometric mean fold rise; nAb, neutralizing antibody; NP, nasopharyngeal; PK, pharmacokinetic; RT-PCR, reverse transcriptase polymerase chain reaction; SAE, serious adverse event; SARS-CoV-2, severe acute respiratory syndrome-coronavirus 2.

4 STUDY DESIGN

4.1 Overall Design

This is a Phase II randomized, open-label, multicenter, dose-ranging study to assess the safety, immunogenicity, PK, and PD profiles of AZD7442 repeat dose regimens. The study will enroll adults and pediatric individuals (≥ 12 years of age weighing at least 40 kg) who are moderate to severely immunocompromised due to an underlying disease or are taking immunosuppressive medications and therefore unable to mount an adequate immune response to COVID-19 vaccine.

Approximately 200 adults and pediatric individuals, who meet the eligibility criteria, will be randomized in a 1:1 ratio to one of 2 AZD7442 treatment arms:

- Arm A (100 participants): AZD7442 600 mg administered intramuscularly (IM) on Day 1 followed by 300 mg IM Q3M for 12 months (a total of 5 doses)
- Arm B (100 participants): AZD7442 1200 mg administered intravenously (IV) on Day 1 followed by 600 mg IM Q6M for 12 months (a total of 3 doses)

An EoT Visit will be conducted at 15 months in both arms (3 months after the final dose of AZD7442).

After the EoT Visit, the participant will enter the follow-up period. Participants will be followed for safety for an additional 9 months after the EoT Visit, ie, through 12 months after the participant's final dose of AZD442.

Participants who permanently discontinue IMP administration due to the premature termination of the study will remain in the study to complete visits/assessments (except those

related to monitoring of IMP administration) for at least 6 months after their final dose of AZD7442.

The total duration of the study for a participant is 105 weeks (approximately 24 months) for both arms which includes the screening period (up to one week), the treatment period (15 months), and the follow-up period (9 months).

An independent DSMB will provide oversight, to ensure safe and ethical conduct of the study (see Section 9.6 and Appendix A 5.1).

The study design is presented [Figure 1](#).

4.1.1 Study Conduct Mitigation During Study Disruptions Due to Cases of Civil Crisis, Natural Disaster, or Public Health Crisis

The guidance given below supersedes instructions provided elsewhere in this CSP and should be implemented only during cases of civil crisis, natural disaster, or public health crisis (eg, during quarantines and resulting site closures, regional travel restrictions, and considerations if site personnel or study participants become infected with SARS-CoV-2 or similar pandemic infection) which would prevent the conduct of study-related activities at study sites, thereby compromising the study site staff or the participant's ability to conduct the study. The Investigator or designee should contact the study Sponsor to discuss whether the mitigation plans below should be implemented.

To ensure continuity of the clinical study during a civil crisis, natural disaster, or public health crisis, changes may be implemented to ensure the safety of study participants, maintain compliance with Good Clinical Practice, and minimize risks to study integrity.

Where allowable by local health authorities, ethics committees, healthcare provider guidelines (eg, hospital policies) or local government, these changes may include the following options:

- **Rescreening:** Additional rescreening for screen failure and to confirm eligibility to participate in the clinical study can be performed in previously screened participants. The Investigator should confirm this with the designated study physician prior to any rescreening during study conduct mitigation.
- **Home or Remote visit in lieu of on-site visit:** Performed by a site qualified HCP or HCP provided by a TPV.
- **Telemedicine visit in lieu of on-site visit:** Remote contact with the participants using telecommunications technology including phone calls, virtual or video visits, and mobile health devices.
- **At-home IMP administration:** permitted only for redosing with no major safety issues after initial dose. Performed by a site qualified HCP, HCP provided by a TPV. Additional information related to the visit can be obtained via telemedicine.

Any modifications or changes in study conduct as a part of mitigation under this section, will be documented as a protocol deviation for tracking purposes.

For further details on study conduct during civil crisis, natural disaster, or public health crisis, refer to [Appendix E](#).

4.2 Scientific Rationale for Study Design

This is a Phase II randomized, open-label study with 2 treatment arms. Randomization will minimize potential bias in dose selection.

The study will enroll adults and pediatric individuals (≥ 12 years of age weighing at least 40 kg) who are moderate to severely immunocompromised due to an underlying disease or are taking immunosuppressive medications and therefore unable to mount an adequate immune response to COVID-19 vaccine.

The primary objective of the study is to assess safety and immunogenicity (ADA) of AZD7442 dose regimens (600 mg IM followed by 300 mg IM Q3M and 1200 mg IV followed by 600 mg IM Q6M) in this population. The repeat dosing treatment regimens with a duration of 12 months will allow for collection of safety endpoints (AEs, SAEs, and AESIs) and ADA data after repeat dosing with AZD7442. A follow-up of 12 months after the participant's last dose will provide additional safety and immunogenicity data on AZD7442.

4.3 Justification for Dose

The loading dose and frequency of repeat dosing in Study D8850C00010 have been chosen taking into account the current prophylaxis dosing schedules approved in PROVENT substudy (D8850C00002; NCT04625725) of 300 mg Q6M and 300 mg Q12M.

The 2 repeat dose regimens planned in this study for 2 different dosing intervals with a loading dose (Arm A: 600 mg IM then 300 mg Q3M; Arm B: 1200 mg IV then 600 mg Q6M) will provide over 18 months of safety and immunogenicity data for serum AZD7442 concentrations ≥ 2 -fold higher than what was needed for at least 6 months of protection against the original SARS-CoV-2 strain and variants of concern in a moderately to severely immunocompromised population due to an underlying disease or are taking immunosuppressive medications. The either 3-month or 6-month repeat administration frequency will inform if immunogenicity differs by administration frequency with similar overall AZD7442 exposure. These data will further inform the safety profile of AZD7442 and will therefore allow for flexibility in dose level and dosing interval of AZD7442 by establishing a wider safety margin for C_{max} and AUC when dosing chronically.

A higher overall dose over a 12-month period will provide safety data for a higher loading dose and higher maintenance dose than have been assessed in clinical studies to date. A

6-month dosing interval at a higher dose of 600 mg IM may minimize the potential risk of ADA.

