ADA, antidrug antibody; AE, adverse event; AESI, adverse event of special interest; GMT, geometric mean titers; GMFR, geometric mean fold rise; nAb, neutralizing antibody; PK, pharmacokinetic; SAE, serious adverse event; SARS-CoV-2, severe acute respiratory syndrome-coronavirus 2.

For exploratory objectives and endpoints, see Section 3 of the protocol.

Overall Design

This is a Phase II randomized, open-label, dose-ranging study to assess the safety, immunogenicity, PK, and PD profiles of AZD7442 repeat dose regimens. The study will enroll adults and pediatric individuals (≥ 12 years of age weighing at least 40 kg) who are moderate to severely immunocompromised due to an underlying disease or are taking immunosuppressive medications and therefore unable to mount an adequate immune response to COVID-19 vaccine.

Approximately 200 participants who meet the eligibility criteria for the study will be randomized in a 1:1 ratio to one of 2 AZD7442 treatment arms:

- Arm A (100 participants): AZD7442 600 mg administered intramuscularly (IM) on Day 1 followed by 300 mg IM every 3 months (Q3M) for 12 months (a total of 5 doses)
- Arm B (100 participants): AZD7442 1200 mg administered intravenously (IV) on Day 1 followed by 600 mg IM every 6 months (Q6M) for 12 months (a total of 3 doses)

An End of Treatment (EoT) Visit will be conducted at 15 months for each arm (3 months after the final dose of AZD7442).

After the EoT Visit, the participant will enter the follow-up period. Participants will be followed for safety for an additional 9 months after the EoT Visit, ie, through 12 months after the participant's final dose of AZD7442.

Participants who discontinue IMP administration due to premature termination of the study will remain in the study to complete visits/assessments (except those related to monitoring of IMP administration; see Section 1.3) for at least 6 months after their final dose of AZD7442.

The study design is presented [Figure 1](#).

Disclosure Statement

This is a parallel-group, safety, immunogenicity, PK, and PD study with 2 arms (both AZD7442 with different dosing regimens) that is not blinded.

Number of Participants

Approximately 200 eligible participants will be randomized in the study to one of 2 AZD7442 dosing regimens: Arm A or Arm B (100 participants per arm).

Intervention Groups and Duration

The AZD7442 dosing regimens to be evaluated in the study are:

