- Arm A: AZD7442 600 mg IM on Day 1 followed by 300 mg IM Q3M for 12 months (ie, Days 92, 183, 274, and 365)

- Arm B: AZD7442 1200 mg IV on Day 1 followed by 600 mg IM Q6M for 12 months (ie, Days 183 and 365)

The total duration of the study for a participant is 105 weeks (approximately 24 months) for both arms which includes the screening period (up to one week), the treatment period (15 months), and the follow-up period (9 months).

Data Safety Monitoring Board

An independent Data Safety Monitoring Board will provide oversight, to ensure safe and ethical conduct of the study.

Cardiovascular Event Adjudication Committee

An independent cardiovascular (CV) Event Adjudication Committee will provide an independent, external, systematic, and unbiased assessment of de-identified blinded data to systematically evaluate CV events.

Statistical Methods

No statistical hypotheses will be tested. Results will generally be summarized by treatment arm using descriptive statistics: frequency and percentages for categorical variables; number of available observations, mean, standard deviation, median, minimum, and maximum, and quartiles where more appropriate for continuous variables.

The final data readout will occur once all participants have completed the follow-up period (at Month 24) or withdrawn due to premature termination of the study.

Primary Endpoints

- The safety and tolerability of AZD7442 will primarily be assessed by the incidence and exposure adjusted incidence of adverse events (AEs), serious adverse events (SAEs), and adverse events of special interest (AESIs).
- The incidence of antidrug antibodies (ADA) to AZD7442 will be assessed and summarized by number and percentage of participants who are ADA positive. The ADA titer will be summarized with descriptive statistics.

Secondary Endpoints

- Individual AZD7442 (tixagevimab and cilgavimab) serum concentration data will be listed and tabulated, along with descriptive statistics. Appropriate PK parameters may be calculated.
- Descriptive statistics for geometric mean titers (GMTs) and geometric mean fold rise (GMFR) in severe acute respiratory coronavirus-2 neutralizing antibodies will include number of participants, geometric mean, geometric standard deviation, 95% confidence interval, minimum, and maximum.

Sample Size

Approximately 200 participants will be randomized to one of 2 AZD7442 dosing regimens: 100 participants to Arm A and 100 participants to Arm B.

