1.3 Schedule of Activities

[Table 1](#) summarizes the SoA for the screening and treatment period for Arm A (AZD7442 Q3M).

[Table 2](#) summarizes the SoA for the screening and treatment period for Arm B (AZD7442 Q6M).

[Table 3](#) summarizes the SoA for the follow-up period for Arm A and Arm B.

[Table 4](#) summarizes the assessments to be conducted when Illness Visits are initiated for participants who are suspected to have COVID-19.

Participants who permanently discontinue IMP administration due to the premature termination of the study will remain in the study to complete visits/assessments (except those related to monitoring of IMP administration) for at least 6 months after their final dose of AZD7442.

- If participants receive their last study drug administration on Day 183 visit, they will complete Day 190, Day 212, and Day 274 (no dosing) visits, followed by an Early Discontinuation visit in place of the Day 365 visit.
- If participants receive their last study drug administration on Day 274 visit, they will complete Day 281, and Day 365 (no dosing) visits, followed by an Early Discontinuation visit in place of the Day 456 visit.
- If participants have already completed visit/assessments up to 6 months after the last IMP administration (i.e. Day 365), the early discontinuation visit will be scheduled as early as possible. However, if early discontinuation scheduling is within one month of last completed in person visit and required samples were collected per protocol, then no additional sample collection is required (with the exception of a urine pregnancy test for WOCBP, and if positive or indeterminant, serum pregnancy will be collected).
- If participants are completing an illness visit series, they will be followed until completion or until the Early Discontinuation visit.

Table 1 Schedule of Activities: Treatment Period – Arm A (AZD7442 Q3M)

Period	Screen ^a	Treatment (Days 1-456)													EoT	For details, see Section
Day (* = IMP dosing day)	-7 to 1	1*	8	29	92*	99	121	183*	190	212	274*	281	365*	372	456	
Week (Month)	-	-	1	4	13 (3M)	14	17 (4M)	26 (6M)	27	30 (7M)	39 (9M)	40	52 (12M)	53	65 (15M)	
Window (days)	-	-	± 3	± 5	± 7	± 3	± 5	± 7	± 3	± 5	± 7	± 3	± 7	± 3	± 15	
P = In-Person Visit RTM = Remote TM Visit ^m	P	P	RTM/ P ^m	P	P	RTM/ P ^m	P	P	RTM/ P ^m	P	P	RTM/ P ^m	P	RTM/ P ^m	P	
Procedure																
Informed consent	X															5.1
Informed assent for pediatric participants	X															5.1

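### Section 4.3 says the arms compare dosing frequency at similar overall exposure, but planned totals are 1800 mg against 2400 mg with different loading doses and first-dose routes; its 18-month data claim also predates the termination

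*Protocol*

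**What the plan says.** Protocol Section 4.3 (Justification for Dose) gives the comparison of the two intervals a specific meaning: it "will inform if immunogenicity differs by administration frequency with similar overall AZD7442 exposure". The same section says that the two planned regimens "will provide over 18 months of safety and immunogenicity data".

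The synopsis sets out the regimens. Arm A is IM throughout: 600 mg at the start, then four maintenance injections of 300 mg, the last of them at one year. For the other arm the synopsis gives "AZD7442 1200 mg IV on Day 1 followed by 600 mg IM Q6M for 12 months (ie, Days 183 and 365"). Section 4.1 and Table 6 agree with these. No section gives a predicted exposure by arm or says what counts as similar.

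On duration, the synopsis describes the full plan: "Participants will be followed for safety for an additional 9 months after the EoT Visit", which itself falls at 15 months. The current version stops dosing permanently. Section 1.3 now spells out two cases. If the last dose was on Day 183, the remaining visits are "followed by an Early Discontinuation visit in place of the Day 365 visit". If it was on Day 274, they are "followed by an Early Discontinuation visit in place of the Day 456 visit". The amendment's own rationale puts the resulting data at 12 months from the first dose.

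ADA incidence is one of the two primary endpoints. SAP Section 4.2.1.3 tabulates it by arm, descriptively.

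**The concern.** To read an ADA difference between arms as an effect of dosing frequency, the arms would have to be alike in the other features that may drive immunogenicity. Section 4.3 says that overall exposure is one of those features. On the protocol's own figures, the arms differ in total dose, loading dose, route of the first dose and frequency, all at once.

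What is at stake is interpretation of a primary endpoint. A study report that carries the Section 4.3 sentence forward could describe a gap in ADA incidence as a frequency effect when it might equally reflect the larger total dose, the larger load or the IV start. In the same way, a reader who relies on Section 4.3 would expect longer ADA and safety follow-up than the amended schedule guarantees.

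**Working it through.** **Inputs.** Doses and days: Protocol synopsis, Section 4.1 and Table 6. Half-life of about 90 days: Section 2.2. Last-dose cases: Section 1.3. IM bioavailability F is not in the documents; it is assumed here to lie between 0.6 and 1.0.

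**1. The plan's own duration figure.** Months = (day − 1)/30.44. The full schedule ends on Day 729: 728/30.44 = 23.9 months, with an ADA sample at that visit. The statement of over 18 months therefore reproduces for the plan before termination.

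**2. Duration now.**
- Last dose Day 183, final visit in place of Day 365: 364/30.44 = 12.0 months.
- Last dose Day 274, final visit in place of Day 456: 455/30.44 = 14.9 months.

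**3. Planned milligrams.**
- Arm A: 600 + 4 × 300 = 1800 mg, all IM.
- Arm B: 1200 (IV) + 2 × 600 (IM) = 2400 mg.
- Ratio B/A = 2400/1800 = 1.33.
- Maintenance rate: 300/3 = 600/6 = 100 mg per month in both arms, both IM.

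**4. Milligrams received after the halt.**
- Both arms stopped at Day 183: A 600 + 2 × 300 = 1200; B 1200 + 600 = 1800; ratio 1.50.
- Arm A stopped at Day 274 (Arm B has no dose that day): A 1500; B 1800; ratio 1.20.

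**5. Exposure.** Milligrams are not exposure, so take a one-compartment model with immediate input, and the same clearance in both arms. AUC to day T is then proportional to the sum over doses of dose × F × (1 − exp(−k(T − t))), with k = ln 2/90 = 0.0077 per day and F = 1 for the IV dose.

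To Day 456, the planned end-of-treatment visit, the fractions in brackets are 0.970, 0.939, 0.878, 0.754 and 0.504 for doses on Days 1, 92, 183, 274 and 365.
- Arm A: F × (582.0 + 281.8 + 263.4 + 226.1 + 151.2) = 1504.4 F
- Arm B: 1163.9 + F × (526.7 + 302.3) = 1163.9 + 829.0 F
- B/A = 0.551 + 0.774/F

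| F | B/A to Day 456, as planned | B/A over Days 183–365, as planned |
|---|---|---|
| 1.0 | 1.32 | 1.12 |
| 0.8 | 1.52 | 1.22 |
| 0.6 | 1.84 | 1.37 |

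The ratio rises as F falls, because only Arm B has an IV dose. Parity would need F = 1163.9/(1504.4 − 829.0) = 1.72, which is above the possible maximum of 1. Adding first-order absorption at an assumed 0.15 per day leaves the Day 456 figures at 1.33 (F = 1.0) and 1.85 (F = 0.6).

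**The case against.** The best case for the sentence is that its subject is the repeat dosing. In that phase both arms receive 100 mg per month by the same route, and with F = 1.0 the modelled exposure over Days 183 to 365 differs by only 12%. This stands, and the fix should keep it. It does not rescue the sentence as written, which speaks of overall exposure; and the twofold loading dose and its route still separate the arms.

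Several further points limit the concern:

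- Section 4.3 does not hide the differences. It refers to a higher overall dose, and it suggests that the longer interval at the higher dose may lower the risk of ADA. A reader might infer that the quoted sentence is the only ADA rationale; it is not.
- A reader might infer a known exposure gap of 80% or more. The documents give no IM bioavailability, so the upper figures rest on an assumption. Without it, the one-compartment model supports about one third as the lower end.
- A reader might infer that the 18-month figure was a miscalculation. It was right for the original plan and is now stale.
- A reader might infer that everyone's follow-up ends at 12 to 15 months, or falls short by 6 months or more. Section 7.4 sets 6 months after the last dose as a minimum, Section 1.3 separately covers participants already past that point, and SAP Section 3.1 still allows for completion at Month 24. The documents do not give the distribution, and the amendment rationale states 12 months from first dose.
- No hypothesis is tested and no frequency effect is estimated. No error rate is affected; the harm is confined to what readers conclude from descriptive tables.

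**Conclusion.** The point holds in a limited form. The claim of similar overall exposure conflicts with the protocol's own regimens: Arm B is planned to receive 33% more drug, and remains 20% to 50% ahead in the two stopping cases worked above. The modelled AUC ratio to Day 456 is about 1.32 at full IM bioavailability and larger at any lower value (1.84 at an assumed 0.6). This rests on the documented half-life, one compartment and equal clearance in the two arms. Total dose, loading dose, first-dose route and frequency differ together, so the study compares two whole regimens and does not isolate frequency.

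The duration statement is a smaller matter: text left unrevised when the study was terminated. Section 4.2 has the same leftover, since it still describes 12 months of follow-up after the last dose.

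Both matters should be corrected because they bear on how a primary endpoint is read. Neither changes conduct, analysis sets or estimates.

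**What to change.** Reconcile Section 4.3, and the post-dose follow-up statement in Section 4.2, with Sections 1.3 and 4.1:

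1. Limit the exposure claim to an equal maintenance dose rate of 100 mg per month.
2. State that the ADA comparison is between whole regimens that differ in total dose, loading dose, first-dose route and frequency, and that it does not isolate frequency.
3. Replace the 18-month statement with the follow-up now obtained, noting that 6 months after the last dose is a minimum.

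If the protocol will not be amended again, the same wording can go in the SAP's section on changes to planned analyses and in the study report.

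Optionally, show cumulative milligrams received beside ADA incidence by arm. SAP Section 4.3.1.2 already summarizes number of doses, and milligrams follow from it because Section 6.6 forbids dose modification. Dose count alone can mislead here, since Arm A has more planned doses (5 against 3) but fewer milligrams.

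The cost is a few sentences, plus one column from dosing data already collected if the option is taken. The stated claim becomes weaker. No dose or clinical rule is proposed.
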